
ensuring child caring practices. Data on morbidity will be collected and necessary medical advice for referral to the health centre will be given equally to each group. The CNP and CNO's time will be mapped and will be asked to adopt study messages to examine the practicality. Data collection, counseling on child caring practice, food demonstration and nutrition education using IEC will be organized and supervised by project staff. It is assumed that if the intervention is successful, and once the nutritional status improves, they are likely to maintain good health. The IEC on dietary practice will be communicated to the VNMC (village nutrition management committee) members for further preventive measures. Data on cost effectiveness of the nutrition education strategies will be collected by a health economist. Data will be analyzed for change in nutritional status from moderate to mild malnutrition or normal nutrition and proportions of children continuing complementary feeding will be compared between the intensive and less intensive intervention and control groups. It is expected that the results of the study will help define the effectiveness of our nutrition education package to prevent and reduce moderate malnutrition existing in large proportion of children in setting with different geographical, and cultural and feeding practices.

KEY PERSONNEL (List names of all investigators including PI and their respective specialties)

Name	Professional Discipline/ Specialty	Role in the Project
1. [name]	Scientist, ICDDR, B	Principal Investigator
2. [name]	Director, CSD, ICDDR,B	Co-Principal Investigator
3. [name]	Senior Medical officer ICDDR, B	Co-Investigator
4. [name]	BRAC, Bangladesh	Collaborative investigator

DESCRIPTION OF THE RESEARCH PROJECT

Hypothesis to be tested:

Concisely list in order, in the space provided the hypothesis to be tested and the Specific Aims of the proposed study. Provide the scientific basis of the hypothesis, critically examining the observations leading to the formulation of the hypothesis.

Hypothesis

- a. Less intensive nutrition education including food demonstration at the community level will be equally effective as intensive nutrition education for the prevention and reduction of moderate malnutrition.
- b. The effect of less intensive nutrition education given over a period of 6 months will sustain during the following six months without any intervention.

Specific Aims:

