The village nutrition management committee will be met at the onset of the study to discuss the objectives of the study, the level and types of input and cooperation that can be mobilized will be planned. A local volunteer will be identified to work for the project selected by the village nutrition committee. Village women's group will meet to plan their time and availability for demonstration and advocacy of measures undertaken for the research projects. The proportion of activity that can be channeled through the CNP and time available for the CNP will be determined. Normally nourished 6-9 month old infants, mild and moderately malnourished children less than 2 years will be taken from the CNP registrar and GMP cards. The proportion of moderately malnourished children with growth faltering and who are receiving supplementary feeding will be excluded from the study. It is known that in health intervention, there is visit effect, where regular visits of health workers indirectly influence caregivers to ask about child's well being and seek advice. To minimize the effect all groups will receive same number of visits for information collection.

Design of the project:

This will be a prospective longitudinal intervention study. The study will have

- a) a management approach and
- b) a preventive approach.

Management approach study groups

- (1) One intervention group of moderately malnourished children without growth faltering will

receive **intensive nutrition education** (INE) and demonstration of appropriate complementary feeding at home in same intensity of recently completed study at Shahrasti thana in Chandpur district. The education will include food demonstration, specific education on diet, components of caring practices, and disease control linking to the referral system.

- (2) The second intervention group will be moderately malnourished children without growth faltering who will receive **less intensive nutrition education** (LINE) food demonstration and specific education on diet, components of caring practices, and disease control linking to the referral system.

Preventive approach study groups

- (3) The third group will be the preventive group with mildly malnourished children and well-nourished 6-9 months aged infants who will receive less intensive nutrition education same as the second group of moderately malnourished children

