- (4) The fourth group will be controls for the preventive group with mildly malnourished children and well nourished 6-9 month aged infants who will not receive any education.

Moderately malnourished children will be included to improve their nutritional status into better nutrition and well nourished and mildly malnourished children will be included to prevent their fall as well as improve in nutrition status.

Details of the nutrition counseling and demonstration of food are given in annex 1.

There will be modification of nutrition education after baseline FGD studies on food perception. The base line weight and length of each child will be recorded. Weight and length will be taken each month for a period of 6 months. Project workers will also take information on anthropometry from the GMP sessions. The main responsibility of education will remain with the health assistant. CNP timing will be mapped and their special training manual will be prepared. They will be trained in different sessions to educate the mothers groups. The sessions with moderately malnourished children and their parents will be organized in consultation with village nutrition management committee (VNMC). The counseling will be based on pictorial or written script in Bangla. Required number of sessions will be planned for increasing the ability to recognize moderately malnourished children. The feasibility will be seen through exploratory meeting with VNMC and moderately malnourished children's mothers.

In the intervention area, **complementary food** will be prepared and demonstrated by the nutritionist and health assistants. Feeding will be encouraged in groups at the community level for initial one month and then it will be encouraged to do at home with supervision of the women support group and health assistants.

Sample size calculation:

Sampling frame: The study subjects will be under 2 years of age and will be recruited from the growth-monitoring program at CNC. Of the total population about 4.5% are under 2 years at a given time. From this population about 10% show growth faltering and come to the CNC for supplementary feeding as the part of the BINP activities. About thirty eight percent children under 2 years of age suffer from moderate malnutrition, about 43.7% are mildly malnourished and about 13.7% are normal according to recent baseline report of BINP.

Sample size for management study group:

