Collection of morbidity data:

Morbidity information will be collected at two weekly home visits during study period using pre-tested questionnaire.

Operational definition

Fever: If the temperature is more than normal, that is above 38.5⁰ C is called fever.

In the field level:

1. When mother tell about her child suffered from fever that lasted for 1 day, a physician will examine the child and child will be treated at home for mild fever.
2. When mother will tell that her child has fever lasting for two to three days, it will be regarded it as moderate fever.
3. Mother will tell that fever lasts for more than three days, he will be examined and regarded as sever fever.

Diarrhoea: An episode of diarrhea is defined as the passage of three or more loose or watery stools within 24 hours. Records will be collected on consistency and the number of stools per day.

1. A child passing loose, liquid or watery stool more than three times per day will be called acute diarrhoea.
2. Presence of blood with stool will be define as invasive diarrhea.
3. When a single episode of diarrhea lasts for more than two weeks, it will be called persistent diarrhoea.

Ear Infection: A child will have pain in ear, fever, with watery or purulent secretion from one or both ear will be diagnosed as ear infection.

Lower respiratory tract infection: When a child suffering from cough and fast breathing more than 50 per minute, fever, or chest indrawing will be defined to have lower respiratory tract infection (LTRI).

Upper respiratory tract infection: A child suffering from cough and cold without sings of LRTI will be diagnosed as upper respiratory tract infection (URTI).

Skin infection: A child suffering from skin disease with impetigo or skin infection or scabies will be define have skin infection.

Sore on Tongue: Ulceration or fissure on tongue or palate will be identified as sore tongue.

Angular stomatitis: Any child having signs of ulceration or excoriation in angle of mouth will be diagnosed to have angular stomatitis.

Xerpthalmia : Conjuntival haziness & corneal haziness will be diagnosed as Xerophthalmia.

The subjects will be referred to THC by interviewers during two weekly home visits if following conditions develop:

Referral will be done accordingly to IMCI criteria in the following ways:

1. Pneumonia: After 2 days of first time of antibiotic therapy:

Check the child for general danger signs.

Assess the child for cough or difficult breathing.

Ask:

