FGD will be conducted on mothers in 6 groups each from 3 CNC's (1 control and 2 study areas). There will be 6-8 mothers of moderately malnourished children in each Focus Group Discussion. This is expected to be more or less homogenous, since mothers having young children in the villages are of similar age FGD will be conducted by the anthropologist. Moderator will play the role of guiding the group on the right topic by putting them on the track. The research personnel will facilitate discussion but they will not influence the discussion. A tape recorder will be used to record the discussion. One facilitator will take notes. Obtained data from FGD will be analyzed manually by using coding.

The FGD will be conducted again to evaluate the change in behaviour and the process indicators. The method indicated above will be followed in the later part of the study.

A pre-test on knowledge of child feeding practice will be done and will be repeated with same the questionnaire after the diet counselling sessions with the mothers. Data on feeding frequency, preparation of information on child feed, dietary ingredients, frequency of feeding and constraints will be recorded at two weekly intervals in study groups. Post test will be conducted at the end of

nutrition education period.

The health assistants will be pre-testing the nutrition knowledge of the mothers and mothers will be observed before actual training is given. These subjects will not be included into study. This will reduce observer bias of the health assistants.

Outcome variables:

1. Mothers understanding and ability to identify moderate malnutrition in children.
2. Mothers understanding on consequence of moderate malnutrition.
3. Change in knowledge of mothers in feeding practices.
4. Frequency of home feeding (Breast-feeding and supplementary feeding).
5. Frequency of seeking medical care during illness, referral, incidence, duration of illness.
6. Adequacy of child feeding, frequency & type of feeding.
7. Weight gain, weight for age and weight for height at the end of intervention.
8. Proportion of complementary feeds in 6-9 months age group.
9. Nutritional status of children at various phases of intervention and observation.
10. Adaptation level of nutrition education program by CNP, CNO.
11. Constant of not practicing education knowledge.

Secondary outcome variables: -

1. Incidence and prevalence of diarrhoea and ALRI
2. Referral success and failure
3. Resistance to education

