4. Food insecurity for child
5. Mothers time constraint for CF preparation
6. CNP time constraints for INE

Process indicators:

5. Number of counseling sessions
6. Proportion of attendance by mothers to counseling session
7. Proportion of attendance of supplementary feeding demonstration session
8. Number of home visits of by Health assistants
9. Use of IEC materials in sessions.
10. Number of community sessions with mothers groups, women's group, and VNMC.
11. Proportion weighing sessions.
12. Member of VNMC meetings.
13. Percent of feeding frequency change.
14. Record of referral.
15. Feeding related behaviour.

Quality control measures:

Quality assurance will include questionnaire development, FGD, intensive staff training, standardization of study procedures, which will be written in detailed manuals, regular staff meetings and supervision by the investigators. The project investigators in 15% random samples will directly supervise systematic data collection. Anthropometry will be standardized at the beginning of monthly sessions by trained nutritionist. External validation of anthropometry will also be done. Validation of nutrition education will be done by attending the sessions by supervisors during group with a check list education and with separate interview. Cross check with mothers for preparation of feeds and feeding frequency will be done by nutritionist. Feeding frequency will be rechecked after the day of interview in 15% of the randomly selected sessions at the household levels. Investigators will make random spot checks and will re-interview at least 15% of mothers on child morbidity on the same day using the same questionnaire. With identification of any discrepancy, the data will be informed to the respective health workers and corrections will be done by supervisor's assistance. Each child will have a record file of important events such as migration, referral, and death and will be kept with project office. The field activity will be communicated to PI by the project supervisors and senior staff by phone or fax in between the visits in the field. Data will be checked by running checking program in computer after collection and before analysis.

Adaptation process of the Community Nutrition Promoters (CNP's) and Community Nutrition Organizer (CNO's):

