1. In this operations research project, we are proposing a community trial in 4 of the BINP thanas in 4 divisions to address the effective and feasible means to prevent and reduce moderately malnourished children and under two years. The Bangladesh Integrated Nutrition Project (BINP) is an initiative of the Government of Bangladesh to reduce severe malnutrition and growth faltering of infants, children under two, and malnutrition in pregnant and lactating women. A recent operations research in Shahrasti thana of Chandpur district has demonstrated significant implementation of moderate malnutrition with intensive nutrition education. It is therefore important to study the feasible means to replicate the nutrition education program for large-scale improvement. To address this issue, an operations research will be undertaken in one thana in each of 4 divisions over an 18-month period. A total of 750 moderately malnourished children will be studied in intensive and less intensive nutrition education groups from 48 community nutrition centers. A group of 380 mildly malnourished children and another group of 100 well nourished 6-9 months old infants will be studied in two groups of less intensive education or no education for preventive effect of nutrition education. The mothers of the first intervention group in moderately malnourished group will receive intensive nutrition education on child feeding, complementary food preparation, and preparation of mixed food household food for first 3 months then will be reinforced for next 3 months. The second intervention group will receive a less intensive education for 3 months then will be reinforced for next 3 months. CNP, CNO s and women group and village nutrition committee will be involved in the process for adoption of the nutrition education for regular program.
2. There is no potential risk to the subject. No blood will be drawn for study purpose.
3. Medical advice will be given to subjects of all groups in the form of enhancing referral to THC of FWC.
4. Privacy of the subject will not be interrupted. All the information will be kept with investigators and will not be available to others.
5. Signed consent form will be obtained from the mothers after explaining them the procedures of the study. The objectives and benefits of the study will also be described to them.

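### The care-seeking and referral outcome does not separate care the caregiver sought from care prompted by study staff, so a true difference between arms is diluted, probably modestly

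*Protocol*

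**What the plan says.** Under Outcome variables, item 5 is "Frequency of seeking medical care during illness, referral, incidence, duration of illness". Secondary outcome 2 is "Referral success and failure", and Process indicators include "Record of referral". Under Quality control measures, each child has a file of important events, referral among them.

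Referral is also part of the randomised intervention. The management groups receive "specific education on diet, components of caring practices, and disease control linking to the referral system". The session tables under Frequency and intensity of the two intervention groups give this topic 12 + 3 sessions in INE and 6 + 3 in LINE. Group 4 of the preventive approach consists of controls "who will not receive any education". The section on adaptation by the CNPs and CNOs counts referral in illness among the maternal behaviours to be changed.

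The study itself also generates referrals and care:

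- Collection of morbidity data: "The subjects will be referred to THC by interviewers during two weekly home visits if following conditions develop". A list of conditions follows. The fever definition in the same section has a physician examine some children whose mothers report fever.
- Project Summary: "necessary medical advice for referral to the health centre will be given equally to each group".
- Annexure 2, item 3: "Medical advice will be given to subjects of all groups in the form of enhancing referral to THC of FWC".

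In contrast, the reply to Reviewer 1 (major suggestion 6) says that nothing extra will be done about morbidity.

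**The concern.** Outcome 5 is meant to show whether education changes what caregivers do when a child is ill. As worded, a visit to the health centre counts equally whether the mother decided on it or an interviewer sent her. The interviewer route runs in all arms. It adds most contacts where caregivers seek care least, because that is where most illnesses remain untreated. The arms are therefore pulled together.

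Two readings are at stake. Between LINE and no education, a real effect of teaching on care-seeking could look smaller than it is. Between INE and LINE, the pull is toward similarity, which on this outcome agrees with hypothesis (a) that the two are equally effective. This is a matter of data capture as well as analysis: if the form does not record who initiated a contact, a later analysis plan may be unable to recover it.

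**Working it through.** The protocol gives no care-seeking rate, effect size or referral uptake, so there is no stated figure to reproduce. The check has two parts: the direction, which follows from algebra, and a range for the size under stated assumptions.

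**Direction.** Let s be the share of illnesses for which the caregiver seeks care unprompted. Let r be the share of the remaining illnesses that reach care only through study staff, assumed equal in all arms.

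- Observed share = s + (1 - s) × r
- Observed difference = (s1 - s0) × (1 - r)

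If s1 = s0, the observed difference is zero, so equal referral creates no spurious effect. If s1 and s0 differ, the difference shrinks by the fraction r.

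**Size of r.** Write r = f × c, where f is the chance that a two-weekly visit falls on a day when the child meets a referral condition and c is uptake of the referral. The 14-day interval is the protocol's. The illness durations and c = 0.6 to 1.0 are assumptions.

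| Illness | Referable days | f | r |
|---|---|---|---|
| 7-day diarrhoea, listed at day 5 | 2 to 3 | 2/14 = 0.143 to 3/14 = 0.214 | 0.143 × 0.6 = 0.09 to 0.214 × 1.0 = 0.21 |
| 4-day diarrhoea | 0 | 0 | 0 |
| 4-day high fever, taken as referable on every day | 4 | 4/14 = 0.286 | 0.286 × 0.6 = 0.17 to 0.286 × 1.0 = 0.29 |

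**What this does to a difference.** Take an assumed 50% v 35% of illnesses with unprompted care, a true difference of 15 points. For power, use 375 per group and the protocol's cluster factor of 1.5, so an effective 375/1.5 = 250 per group, with a two-sided 5% test. This treats each child as contributing one illness.

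| r | Observed difference | Power |
|---|---|---|
| 0 | 15.0 points | 93% |
| 0.10 | 15 × 0.90 = 13.5 points | 86% |
| 0.25 | 15 × 0.75 = 11.25 points | 72% |

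These figures are illustrative only. The trial was not sized on this outcome, and the true denominators would be illness episodes.

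**The case against.** The strongest reply is that the study's referral is narrow. Staff act on a list, and that list leaves out several recorded conditions: upper respiratory infection, skin infection, sore tongue and angular stomatitis. The pneumonia and dysentery entries are written as follow-up checks after earlier care, so a staff referral there seldom creates a first contact. This stands, and it limits the size.

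A reader might infer that every sick child found at a visit is referred. A 7-day illness would then give f = 7/14 = 0.5, and 30% to 50% of the difference would be lost at 60% to 100% uptake. The documents do not support that, since only listed conditions trigger referral. Full uptake is also doubtful: Annexure 4 reports that obtaining service at the thana health centre remained a problem in the earlier study, and the reply to Reviewer 1 describes the referral system as not yet well under way. However, the general referral advice promised to all groups is not tied to the list, so the list does not cap staff influence entirely.

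A second reply is that equal visits and equal referral are deliberate and fair. They are: they protect against a false difference. They do not preserve a true one.

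A third reply is that referrals are already recorded in the child's file and as a process indicator, and that the questionnaire, which is not shown, may capture who initiated a contact. It may. The protocol does not say so, and outcome 5 is not defined in those terms.

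Finally, care-seeking is part of one item among eleven outcomes, and the Data Analysis section names no comparison of it. This keeps the point minor.

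**Conclusion.** The point holds as a minor one. Outcome 5 mixes caregiver-initiated care with care prompted by the study, and a true between-arm difference is diluted by (1 - r). The size cannot be derived from the documents. Under the assumptions shown, the loss is about 9% to 21% for a 7-day diarrhoea and none for a 4-day one, with possibly more for high fever. The formula assumes that r is equal across arms; if education also raised uptake of staff referral, the loss would be smaller.

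Two stronger conclusions do not follow. A null result is not built in: even with r = 0.5, an assumed 40% v 20% would be observed as 70% v 60%, still 10 points apart. Nor is the main comparison directly affected: the hypotheses and sample size concern malnutrition, and weight and nutritional status are not defined through care contacts. Referring sick children protects participants and is not the fault. The fault is that the outcome is not defined apart from it.

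**What to change.** 1. On the existing two-weekly form, code each care contact as caregiver-initiated (before or without a study referral or advice about that illness) or as following a study referral or advice. Teaching in the scheduled sessions should not count as a referral, because it is the intervention being tested.
2. Under Outcome variables, define the care-seeking part of item 5 as caregiver-initiated care per illness episode.
3. Report study-initiated referrals and their uptake separately, under secondary outcome 2 and the referral process indicator.
4. Reconcile the reply to Reviewer 1 on morbidity with the Project Summary, the morbidity section and Annexure 2, so that it is clear what the study does in each group.

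The referral of sick children stays unchanged. The cost is one extra code on a form already in use and one line in the outcome list. The limitation is that the coding relies on the caregiver's recall of who prompted the contact; the referral entries in the child's file, if dated, would allow a check.
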